#### **9.0 PLANS FOR PUBLICATION**

Study results will be submitted to a peer-reviewed journal for publication. This study will also be listed on Clinicaltrials.gov and study results will be posted in accordance with appropriate regulations and ICJME requirements.

Neither the complete nor any part of the results of the study carried out under this protocol will be published or passed on to any third party without the consent of the study sponsor-investigator. Any investigator involved with this study will be obligated to provide the sponsor-investigator with complete results and all data derived from the study.

## 11.0 APPENDICES

**READER STUDY:** Evaluation of a Carbon Nanotube Enabled Solid-State Head CT

Subject ID: \_\_\_\_\_

Reader: \_\_\_\_\_

Date: \_\_\_\_\_

1) Hemorrhage: \_\_\_\_\_ Yes \_\_\_\_\_ No  
Hemorrhage confidence 0-100% in 10% increments: \_\_\_\_\_ %  
Location (lobe): \_\_\_\_\_

2) Fracture: \_\_\_\_\_ Yes \_\_\_\_\_ No  
Fracture confidence 0-100% in 10% increments: \_\_\_\_\_ %  
Location (bone): \_\_\_\_\_

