## **3.0 PATIENT ELIGIBILITY**

### **3.1 Inclusion Criteria**

[figure not shown]
- 3.1.1** 18 years of age or older
- 3.1.2** Medically stable ambulatory patient (outpatient) with head trauma or known intracranial hemorrhage (subdural or intraparenchymal) or skull fractures
- 3.1.3** Patient has undergone conventional head CT imaging at UNC hospitals within the past 5 days or will undergo a CT scan of the head
- 3.1.4** Willing and able to provide written informed consent

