#### 4.2.4 Reader Study

All images will be de-identified before inclusion within a reader study. We will perform a reader study with physician readers comparing the acquired imaging s-HCT images and conventional head CT. We hypothesize that the sensitivity of reader's in the interpretation of images from the s-HCT system will be similar to that of the conventional CT imaging. The paired images will be presented to five readers. Readers will be blinded to which imaging modality is being presented. There is, however, readers may be able to distinguish the imaging modality based on the images. Our readers will consist of a trauma surgeon, neurosurgeon or neuro radiologist and non-study radiologists to better reflect the different clinical backgrounds that may be available in a Role 3 environment.

Reconstructed images will be presented in a clinical PACS environment. The readers will be presented images for interpretation in a two-phase study with an interim washout period. First, for each patient, either the s-HCT or conventional head CT images will be presented in random order, and the readers will be asked to identify the presence of hemorrhage (yes/no), the location of the pathology if present and confidence level (0 through 100% in 10% increments). Readers will also be asked to perform interpretations with the appropriate Imaging CT CDE, including the Marshall CT TBI classification code 30, hemorrhage and fracture elements. Four weeks later, the other modality for each patient will be presented in a random order and the same scoring obtained.

The scoring scheme used by readers will include 1) hemorrhage (yes/no) with confidence 0-100% in 10% increments, 2) fracture (yes/no) with confidence 0-100% in 10% increments, 3) streak artifacts (yes/no), and ) other artifacts (yes/no).

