### 7.3 Data Analysis Plans

We will estimate the sensitivity and specificity from the two modalities. To compare the results from the two imaging modalities, we will adopt the mixed effect ANOVA based on the Dorfman-Berbaum-Metz method. To test the main hypothesis, the F-test statistic from the model parameter estimates will be used to compare the mean sensitivity / specificity metrics between the conventional head CT and the simulated solid-state head CT. Possible interactions between the modalities and the readers and the hemorrhage type/locations will also be included and tested for statistical significance. Sensitivity and specificity on the presence of clinically actionable pathology will also be assessed, based on consensus read of the conventional imaging.

For each confidence comparison, the average confidence scores and the corresponding standard deviations will be reported. To test whether the mean

confidence score is larger than zero, a linear mixed effect will be used to analyze data, where the outcome variable is the confidence scores collected in this study and only a grand mean parameter is in the independent list. Additionally, a random intercept is used in the model to account for the correlation among readers when reading the images from the same patient. The Wald's test based on model fit will be used to test whether the grand mean parameter is larger than zero. When the p-value from this test is less than 0.05, it will be concluded that there exists significant evidence that readers have more confidence with the s-HCT modality compared to the other modality. ROC curves will be evaluated.

We will also descriptively compare inter-reader agreement by modality for image quality, confidence in image interpretation, presence and location of hemorrhage, and presence and location of fractures by computing and reporting Fleiss' kappa.

All statistical estimates of population parameters will be tabulated along with corresponding confidence intervals (CIs) and/or standard errors (SEs) to convey levels of precision / imprecision. Hypothesis tests that are deemed to be not statistically significant will be indicated as inconclusive.

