**Rotterdam CT Scale using sHCT**

## 1. Basal cisterns

0	1	2
Normal	Compressed	Absent

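### The reader form records hemorrhage site by lobe only, without side or compartment, so the planned location kappa would be coarse; the form also carries Rotterdam where section 4.2.4 names Marshall

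*Combined protocol and SAP*

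**What the plan says.** **What readers record.** Section 4.2.4 asks for hemorrhage yes/no and then "the location of the pathology if present and confidence level". It gives no coding scheme for site. It also asks for interpretation with the imaging CT common data elements, "including the Marshall CT TBI classification code 30, hemorrhage and fracture elements".

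**The form.** Section 11.0 gives one reader form. Item 1 is hemorrhage yes/no, a confidence percentage and a blank headed "Location (lobe". Item 2 is the same for fracture, with a blank for the bone. A block titled "Rotterdam CT Scale using sHCT" follows. It includes an item for epidural mass lesion and one for intraventricular or traumatic subarachnoid blood. Image quality, artifact items and free-text comment lines close the form. It has no Marshall item.

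**Who is enrolled.** Section 3.1 admits patients with head trauma, skull fracture or "known intracranial hemorrhage (subdural or intraparenchymal" bleeding.

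**What is analysed.** Section 7.3 lists, for a descriptive comparison of reader agreement by modality, "presence and location of hemorrhage, and presence and location of fractures by computing and reporting Fleiss' kappa". For the comparison of sensitivity and specificity it adds: "Possible interactions between the modalities and the readers and the hemorrhage type/locations will also be included and tested for statistical significance".

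**The concern.** Fleiss' kappa needs each reader's answer placed in a defined category. For hemorrhage location the form offers one category system, the lobe, and that system does not fit the patients being enrolled. Subdural blood lies outside the brain, so readers who see the same collection may name different lobes or write something else. The form does not ask for side, so readers who place a bleed on opposite sides of the head may leave identical entries. The first problem lowers measured agreement and the second raises it, so the resulting kappa is hard to interpret.

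Three smaller gaps concern the same form. Section 4.2.4 and the form name different severity scales. Item 1 does not say whether it includes the bleeds asked about in the Rotterdam block. Section 7.3 does not say where the type and location variable in the interaction test comes from. At stake are one descriptive agreement result, one covariate and a contradiction in data collection. The primary endpoint is not at stake.

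**Working it through.** The plan gives no figure for this point. The power calculation in section 7.2 does not involve the form. The check is a comparison of what is planned with what is collected, plus one illustration.

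**1. Planned use against form field**

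| Planned use | Field on the form |
|---|---|
| Hemorrhage yes/no (primary, 2.1) | Item 1, explicit |
| Fracture yes/no (2.2) | Item 2, explicit |
| Confidence (2.2, 7.3) | Items 1 and 2, explicit |
| Kappa, image quality (7.3) | Item 6 of the Rotterdam/quality block, explicit |
| Kappa, hemorrhage location (7.3) | Free text by lobe; no side, no compartment, no coding rule |
| Kappa, fracture location (7.3) | Free text by bone; no side |
| Interaction with hemorrhage type/location (7.3) | No subdural or intraparenchymal field; source not stated |
| Marshall class (4.2.4) | None; Rotterdam instead |

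The form does carry some type information, because epidural and intraventricular/subarachnoid blood have their own items. The missing types are subdural and intraparenchymal, the two named in section 3.1.

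**2. How lobe-only coding moves agreement**

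For one patient read by n = 5 readers (section 4.2.4), the agreement term in Fleiss' kappa is

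P = (sum of squared category counts - n) / (n(n - 1)), with n(n - 1) = 20.

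The 3-to-2 splits below are assumed, to show the mechanism.

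- *Intraparenchymal bleed: three readers place it left frontal, two right frontal.* Coded with side: (9 + 4 - 5)/20 = 0.40. Coded by lobe alone: (25 - 5)/20 = 1.00.
- *Subdural collection: all five readers see it on the same side; three write frontal, two parietal.* Coded by lobe: (9 + 4 - 5)/20 = 0.40. Coded by compartment and side: (25 - 5)/20 = 1.00.

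The error can therefore go either way. Its net size cannot be computed. It depends on how many patients have extra-axial bleeds, how often readers disagree on side, and how often they write the side unprompted. The documents give none of these.

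**3. Extent**

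50 patients x 5 readers x 2 modalities = 500 planned reads. This is the number of forms to be completed, not a measure of bias. Only forms with a positive call carry a location.

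**4. Source of type and location for the interaction**

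- Sections 2.3 and 4.2.3 provide a three-month clinical reference standard. Section 4.2.3 describes it in terms of whether a hemorrhage or fracture was present; type and side are not mentioned.
- Section 7.3 also mentions a consensus read of the conventional images.
- Sections 4.2.4 and 8.3.1 refer to imaging common data elements, but section 4.2.3 limits the set to three modules, none of them named as imaging. No imaging data-element form is shown.

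Several sources are possible, and the plan names none of them.

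**The case against.** The location line is an open blank, not a tick list. A reader may write a side, list two sites or describe a subdural in words, and there is space for comments. A reader might infer that every opposite-side disagreement will be scored as agreement, or that a subdural has no possible answer. The documents do not support either: the form fails to prompt for these details but does not prevent them.

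The interaction test does not need type from the readers. A reader who misses a bleed cannot state its type, so in a sensitivity model the natural source is the patient-level reference standard. Type is also not on the kappa list. A reader might infer that the type, location and agreement results will be wrong or unavailable; that goes too far. Agreement on presence, image quality and confidence has proper fields, fracture location has a bone field, and location kappa can be computed by lobe.

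The page in the appendix may not be the only instrument. Section 4.2.4 asks readers to complete the imaging data elements, and section 8.3.1 sends such data to REDCap. So it is not shown that Marshall will go uncollected, only that this page lacks it. Neither scale appears in the objectives or in section 7.3.

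These objections stand, and they limit the point. They do not supply a side or compartment prompt, a coding rule for the location kappa, or agreement between section 4.2.4 and the form. A patient-level type variable cannot serve the location kappa, which needs each reader's own coded answer.

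**Conclusion.** The point holds as a modest, cheap improvement. Followed literally, the form gives a coarse kappa for hemorrhage location, with possible error in both directions and a net size that the documents do not allow one to estimate. The naming of Marshall in section 4.2.4 and Rotterdam on the form is a plain contradiction to be reconciled, but it changes no planned analysis.

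A reader might also infer that the primary call is compromised, because someone could tick no hemorrhage in item 1 and still mark blood in Rotterdam items 3 or 4. The documents do not support that. The hemorrhage call has its own explicit yes/no field and nothing lets another item override it, so the primary sensitivity remains computable. A contradictory form would be an ordinary data query, and one sentence on the scope of item 1 would make it rarer.

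The conclusion assumes that the form shown is the one used for location, that sides are not consistently volunteered, and that some enrolled patients have extra-axial bleeds. Section 3.1 makes the last likely.

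**What to change.** Before reads start:

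- Replace the hemorrhage location line with compartment (epidural, subdural, subarachnoid, intraventricular, intraparenchymal) and side, with lobe for intraparenchymal bleeds only. Allow more than one entry.
- Add side to the fracture bone field.
- State in section 7.3 that hemorrhage location agreement is computed on compartment plus side. Because several entries are allowed and Fleiss' kappa takes one category per reader, compute it for each compartment-side cell as present or absent.
- Name one severity scale in both section 4.2.4 and the form.
- State on the form that item 1 covers any intracranial hemorrhage, including those in Rotterdam items 3 and 4, and add a REDCap check for contradictory entries.
- State in section 7.3 that hemorrhage type and location in the interaction come from the reference standard, and have the record abstraction in section 4.2.3 capture them.

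The cost is a revised form, matching wording in sections 4.2.3, 4.2.4 and 7.3, and a few more seconds per read. No extra patients or visits are needed.

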**Rotterdam CT Scale using sHCT**

## 1. Basal cisterns

0	1	2
Normal	Compressed	Absent

## 2. Midline Shift

0	1
No Shift or Shift $\leq$ 5 mm	Shift $>$ 5mm

## 3. Epidural Mass Lesion

0	1
Present	Absent

## 4. Intraventricular blood or traumatic Subarachnoid hemorrhage (tSAH)

0	1
Absent	Present

## 5. Sum score (+1): \_\_\_\_\_

## 6. Image Quality

1	2	3	4	5
Non-interpretable; Artifact present;	Artifact present; moderately interferes with	Artifact present; mildly interferes with interpretability	Artifact present; does not interfere with	High quality, no artifacts

severely interferes with interpretability	interpretability		interpretability	
---	------------------	--	------------------	--

7. Streak Artifacts:  Yes  No

Location (lobe): \_\_\_\_\_

8. Other artifacts:  Yes  No

Location (lobe or  
bone): \_\_\_\_\_

Reader comments regarding the images:

---

---

Reader comments regarding artifacts:

---

---

---
